COMIRB Protocol

Version Date: 12-14-2017

COLORADO MULTIPLE INSTITUTIONAL REVIEW BOARD
 [name] [contact] [contact]

Project Title: Prevention of enamel demineralization in fixed appliance orthodontic patients using UDMA-K18 sealant to prevent microbial attachment. A randomized split mouth clinical trial.

Principal Investigator: [name], Professor and Director of Translational Research
Orthodontics Residents: [name] and [name]

[name] is the research mentor for University of Colorado, School of Dental Medicine, Department of Orthodontics residents Drs. [name] and [name]. Drs. [name] and [name] will be performing all the sealant and bracket placements. [name] will assist in the histology and evaluation of the extracted teeth.

- I. **Hypotheses and Specific Aims:** The hypothesis is that UDMA-K18 containing smooth surface sealant will be more effective at reducing enamel demineralization than the UDMA control or no treatment. This study will assess the effect of a quaternary ammonium methacrylate (QAM) called K18 antimicrobial compound tethered to urethane dimethacrylate resin (UDMA-K18). This resin will be tested against UDMA sealant and no sealant. This study will evaluate effectiveness of a UDMA-K18 sealant to prevent biofilm attachment to tooth surfaces thereby eliminating the possibility for the tooth to be demineralized.

- II. **Background and Significance:** Far too frequently orthodontic patients are unable to perform sufficient oral hygiene to remove all of the bacterial biofilm surrounding orthodontic brackets. When the bacterial biofilm is not removed, tooth demineralization is possible. The incidence of new tooth demineralization, often called white spot lesions (WSL), has been studied at the University of Colorado Department of Orthodontics. Forty-four orthodontic patients ages between 11 and 21 years of age were assessed over the course of their therapy for the development of new WSL. This study reported that 84.6 % of the patients developed new WSL, and the total area of WSLs also increased from $16.6 \pm 23.6 \text{ mm}^2$ per patient to $42.6 \pm 50.7 \text{ mm}^2$ per patient. The period of therapy where the greatest increase in WSL occurred was between initial banding and 1 year of therapy. The area most susceptible to WSLs during treatment is the cervical third, and both anterior and posterior teeth are equally susceptible to the development of new lesions. (Faranesh et al., 2017). Given that the bacterial biofilm is

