- e. The methods described in the paper by Schmuck and Carey (2010) will be used for the transverse microradiography (TMR) of the samples in this study. The extracted teeth will be sectioned and digital images will be taken with incident and transmitted polarized light to visualize any lesion in the sample. TMR will be used to determine surface lost. TMR determination of lesion depth will be used to compare the measurement via polarized light microscopy.

IV. Research Methods:

- a. **Outcome Measures:** mineral density profile and lesion depth of extracted teeth in these experiments. Mineral density will be measured by transverse x-ray microradiography (Schmuck and Carey, 2010), lesion depth will be measured by polarized light microscopy (Wefel and Harless, 1984; Darvishiabyaneh and Carey 2016; and for orthodontic evaluations Lee *et al.*, 2015).

- b. **Description of Population to be Enrolled:**

Research participants will be between 12 and 89 years of age who are subjects undergoing orthodontic treatment at the Department of Orthodontics Clinic, School of Dental Medicine, University of Colorado. The following inclusion criteria will be applied: comprehensive fixed orthodontic treatment with brackets from at least second premolar to second premolar, treatment planned already for the extraction of at least 3 bicuspids (any combination), patient at the University of Colorado School of Dental Medicine Orthodontic Clinic, can place bracket base on teeth to be extracted for at least 1 month

prior to extractions, no previous white spot lesions, caries or restorations present on the facial surface of the teeth being studied, adequate oral hygiene.

In the recruitment process the attending resident will provide information and answer any questions about the study to the potential study participant. If there is interest on behalf of the patient then the consent form will be reviewed and after presentation the form will be signed by all who wish to join the study. The consent form is attached as a separate document. There is no benefit to the patient to participate other than participating in a study that may find a beneficial treatment for others in the future. There will be no effect on the patients treatment or experience should they decide not to participate or to participate.

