(experimental group). The number of patients required for this study was calculated from studies that had a similar design (de Moura *et al.*, 2006; Uysal *et al.*, 2010). De Moura *et al.* studied the effect of a fluoridated antiplaque dentifrice on the development of caries lesions adjacent to orthodontic brackets. Fourteen orthodontic patients with planned extractions were divided into two groups of 7. The patients used experimental or control toothpastes 3 times per day for 28 days. The teeth were extracted and the mineral loss was determined in the cross-sections by use of microhardness. The results showed that there was a statistically significant ($p < 0.05$) improvement with the experimental antiplaque toothpaste for the first 10 μm of depth. There was no significant difference at deeper distances from the surface. A calculation of their experimental power shows that an n of 7 per group is insufficient to achieve 80 % power at an α of 0.05. Additionally, the microhardness method is less sensitive to mineral density loss than the TMR methods to be used in this study. Balancing the increased sensitivity via TMR with the insufficient power in the de Moura study to make conclusions about the efficacy of the antiplaque toothpaste to prevent tooth loss; we opt to be more conservative and use a larger n per group. Based on the previously observed variations in mineral density and clinically relevant minimum difference of 10 % mineral density in the first 50 microns of tooth surface between the negative control and the experimental K18-UDMA sealant, the number of subjects to achieve 80 % power at an alpha of 0.05 is 20 subjects. It is anticipated that up to 30 patients may be recruited to this study, with 20 needed for statistical power to answer our research question.

2. If the patient has a fourth bicuspid is planned for extraction, a random treatment will administered to this last tooth. This will provide additional information on the effect of location (upper or lower jaw) on the protective ability of the experimental sealant.

- ii. Teeth planned for extraction will be bonded with a bracket pad using one of three systems: no treatment (negative control), UDMA sealant (control) and K18-UDMA sealant (experimental group). The bracket pad does not have the bracket protruding from the base.
 - 1. Blinding:

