5. The use of smooth sealants on the teeth to be extracted is not unique as many patients have a smooth surface sealant placed after the orthodontic brackets are placed. There are several commercial products that release fluoride specifically for the purpose of prevention of WSL. It is unfortunate that there are few well designed studies about the use of these sealants.
6. Should the patient decide to withdraw from planned orthodontic therapy prior to extractions, the bracket pads can be removed following the standard procedures for removing brackets at the same time as the brackets are removed. The sealants will come off at the same time because the standard procedure includes polishing the tooth surfaces when brackets are removed.
7. Patient identification is only to identify which tooth received the specific treatments so that when the teeth are extracted by the oral surgeon the groups can be identified. No patient information is associated with the outcome measures.

- ii. Justification of Procedures: There are no procedures delivered to the patient that are not within the scope of the standard procedures for orthodontic patients. All data is gathered from the extracted teeth in the laboratory.
 - iii. Data Collection Tools: Mineral density and lesion depth will be determined in the laboratory through histological examination of the teeth. Briefly, the teeth are cross-sectioned through the bracket pad to generate a 1 mm thick slab from the middle of the tooth. This slab is observed under polarized light microscopy to measure the lesion depth (if any) from the surface, and subjected to x-ray to determine the mineral density across the lesion.
- e. **Potential Scientific Problems**: None are anticipated.
- f. **Data Analysis Plan**
- i. Statistical analysis will include graphical evaluations, along with descriptive statistics (mean, standard deviation), and one-way ANOVA for the three groups for both mineral density and lesion depth outcomes. If appropriate, there will be follow-up ranked comparison testing at a significance of $P \leq 0.05$. There will be paired-t tests between UDMA and negative controls, UDMA-K18 and negative controls, and paired-t tests between UDMA and UDMA-K18 sealants on mineral density and lesion depth outcomes. Should there be data from a 4th tooth (2 teeth will receive the same treatment) the data from the 2 teeth with the same treatment will be averaged prior to comparison to the controls.

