 - ii. The possibility of regional variations (left vs. right, upper vs. lower) has been taken into account in the calculation of the size of the patient cohort. The sample number calculation was based on differences and variations that are relatively large, and an additional 10 (50 % number) patients were added to the cohort to give the strongest probability of being able to make statistically based conclusions.
 - iii. Secondary analyses may be possible to assess the ability of microbial biofilm to cause demineralization differences between upper and lower arches. If a patient has a fourth bicuspid that is to be extracted (which is usually the case) the assignment of one of the

[figure not shown]
three treatments will be to generate a pair (left vs. right or upper vs. lower) for comparison. The statistical analyses will include paired-t tests for the differences that may be observed within each treatment group.

[figure not shown]
- g. **Summarize Knowledge to be Gained:** Whether the use of UDMA-K18 sealant prevents tooth demineralization during orthodontic therapy.
- i. This is not a pilot study, and is intended to provide the clinical efficacy of the UDMA-K18 sealant to prevent white spot lesions around orthodontic brackets. Unless the variation is much larger than anticipated there will be sufficient power in the experimental design to make statistically based conclusions about the sealant efficacy. One of the experimental design features is that each patient will have all the controls and the experimental sealant so paired differences within each patient will be determined. This sort of paired difference experimental design is one of the most sensitive
 - ii. The data generated and the conclusions achieved will be useful for the dental industry to decide whether to commercialize the sealant.

References:

- Gong S-Q, Niu L-N, Yiu CKY, Rhou H, Qi Y-P, Blissard JD, Nikonov S, Brackett MG, Messer RLW, Wu DC, Jao J, Brister LB, Rueggeberg FA, Arola DD, Pashley DH, Tay FR. Quaternary ammonium silane-functional, methacrylate resin composition with antimicrobial activities and self-repair potential. *Acta Biomaterialia* 2012;8:3270-3282.

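### The contrast the trial was sized on is never named primary, and six paired t-tests on two unranked outcomes have no order, multiplicity rule or definition of success

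*Combined protocol and SAP*

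**What the plan says.** **Hypothesis (section I).** The K18 sealant "will be more effective at reducing enamel demineralization than the UDMA control or no treatment". The conjunction leaves open whether one comparison or both must succeed.

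**Outcomes (IV.a).** These are "mineral density profile and lesion depth of extracted teeth in these experiments", with no ranking.

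**Sample size (IV.c.i.1).** The calculation uses a difference of "10 % mineral density in the first 50 microns of tooth surface between the negative control and the experimental K18-UDMA sealant" and concludes that "the number of subjects to achieve 80 % power at an alpha of 0.05 is 20 subjects". Up to 30 patients may be recruited, "with 20 needed for statistical power to answer our research question". No standard deviation (SD) and no sidedness are given.

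**Analysis (IV.f.i).** The plan lists "one-way ANOVA for the three groups for both mineral density and lesion depth outcomes", then an unnamed ranked follow-up if appropriate, at P ≤ 0.05. Separately it states "There will be paired-t tests between UDMA and negative controls, UDMA-K18 and negative controls, and paired-t tests between UDMA and UDMA-K18 sealants", for both outcomes. The paired tests are not conditional on the ANOVA, and no order, alpha split or success rule is attached to them.

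**Other analyses (IV.f.iii).** Only the arch comparisons are labelled secondary: "Secondary analyses may be possible to assess the ability of microbial biofilm to cause demineralization differences between upper and lower arches".

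**Blinding (IV.c.ii.1).** The statistical evaluation is blinded to which sealant is A and which is B until the evaluations are complete.

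**Purpose (IV.g).** The trial is described as not a pilot. Its conclusions are meant to help industry decide on commercialization.

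**The concern.** A lead test is implied by the sample-size paragraph, but the analysis section does not pick it up. It gives the sized contrast the same standing as the other five paired tests, and it does not carry over the 50-micron summary of the density profile. A reader of the results could not tell from the plan which finding decides efficacy: K18-UDMA against no sealant, K18-UDMA against UDMA, either, or both, and on density, depth, or either.

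This matters for two reasons. First, the chance of a false K18 claim depends on which success rule is adopted, and the plan fixes none. Second, the sized contrast compares coating plus K18 with bare enamel. On its own it cannot show that K18 adds anything to the resin. Only K18-UDMA versus UDMA does that, and the plan does not say what role that test plays.

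**Working it through.** **1. Count of tests.** 3 contrasts × 2 outcomes = 6 paired t-tests. K18-UDMA appears in 2 contrasts × 2 outcomes = 4 of them.

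**2. The plan's own figure.** N = 20 cannot be reproduced forwards, because the SD is missing. Solved backwards for a two-sided paired t-test at 0.05 (an assumption), power = P(|T| > t₀.₉₇₅,₁₉), where T is noncentral t with 19 df and noncentrality d√20. Setting power to 0.80 gives d = 0.660. If 10 % is read as 10 points, the implied SD of paired differences is 10 / 0.660 ≈ 15.1 points. The documents give nothing to check this against. A two-sample reading with 20 per group implies a per-group SD of 11.0 instead.

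**3. Assumptions for the error rates (not in the documents).** Each paired t-test is two-sided at 0.05, n = 20, data are normal, there is one tooth per treatment, correlation among the three teeth is equal, and the correlation between the two outcomes is 0, 0.5 or 0.8. Rates come from 200,000 simulated trials per setting, except the rates in step 5, which come from 60,000.

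**4. All three arms equal; success means any one K18 test favours K18.**
- One test, K18 direction only: 0.05 / 2 = 2.5 %.
- Four such tests if independent: 1 − 0.975⁴ = 9.6 %.
- Simulated, allowing for the shared K18 tooth and the outcome correlation: 8.9 %, 8.2 % and 7.1 % at correlations 0, 0.5 and 0.8.

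**5. All three arms equal; success means K18 beats both controls on the same outcome, for at least one outcome.** Simulated: about 0.7–0.9 %.

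**6. The coating works and K18 adds nothing.** Both sealants are better than no sealant by d = 0.660 on both outcomes, with the same success rule as step 5. When K18-UDMA falsely beats UDMA it nearly always beats no sealant too, so with independent outcomes the rate is close to 1 − 0.975² = 4.9 %. Simulated: 4.9 %, 4.5 % and 3.9 %. With one endpoint and a fixed order the rate is 2.5 %.

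**7. Power cost of alternatives, at the implied d = 0.660.**

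| Rule for the sized contrast | n = 20 | n = 30 |
|---|---|---|
| Single primary test at 0.05 | 80 % | 94 % |
| Bonferroni over six tests (0.05 / 6 = 0.0083) | 52 % | 78 % |

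**The case against.** **The sample-size paragraph makes the primary test obvious.** It does point to one, and this stands as mitigation. But no section designates it, and IV.f.i lists all three contrasts on both outcomes without distinction.

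**The ANOVA protects the paired tests.** The text does not make it a gate. If it were one, the all-arms-equal rate of a false K18 benefit would fall to 3.3–4.0 % with a within-patient ANOVA. It would fall to 0.3–0.4 % with a literal one-way ANOVA and an assumed tooth correlation of 0.5, and such a gate would also cost power. The inflation in step 4 therefore depends on reading the paired tests as unconditional, which is how they are written.

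**Blinding prevents picking a favourable test.** It limits this during analysis. It does not say which result counts once the code is opened.

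**The familywise error is over 20 %.** A reader might infer this, since the chance of any false positive among the six tests is 23 %, 22 % and 19 % under the step 3 assumptions. That figure includes UDMA versus no sealant, which is not a K18 claim, and results in both directions. It overstates the risk of a false K18 claim.

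**K18-UDMA versus UDMA is underpowered.** A reader might infer this as well, but the documents do not support it. With the SD implied in step 2, power at n = 20 is 80 %, 56 % or 29 % if K18's added effect is all, three quarters or half of the sized difference. With the two-sample reading and a tooth correlation of 0.7, it is 99.9 %, 96 % or 70 %. With no SD given, neither set can be preferred. The general power statement in IV.g.i is conditional on the variation not being much larger than expected, and it can be read as referring to the sized contrast.

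**Conclusion.** The concern holds. The plan implies a lead test but does not designate one. It runs six paired t-tests on two unranked outcomes without an order or multiplicity rule, and it does not define success. This textual gap does not depend on any assumed SD.

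Its size depends on the success rule. A false K18 benefit occurs in about 7–9 % of trials if any of the four K18 tests counts and all arms are equal, against 2.5 % for one test. If both controls must be beaten on the same outcome, the rate is about 0.7–0.9 % when all arms are equal. It is about 4–5 % when the coating works and K18 adds nothing, against 2.5 % under a fixed order. These rates rest on the assumptions in step 3 and on the paired tests not being gated; the 4–5 % also uses the effect size implied in step 2.

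The point does not show that 20 patients is the wrong number or that K18-UDMA versus UDMA lacks power. It should be fixed before the code is opened. The design itself stands.

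**What to change.** Add to IV.f.i:

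> The single primary test is UDMA-K18 versus no sealant on mean mineral density over the first 50 microns (paired t-test, two-sided 0.05). Only if it is significant, UDMA-K18 versus UDMA is tested on the same endpoint at two-sided 0.05, and any claim about K18 itself requires this second test. All other tests, including lesion depth, are secondary or descriptive. All tests are computed under the Sealant A/B code, and the order is applied when the code is opened.

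The last sentence is needed because the second step requires knowing which sealant contains K18, and IV.c.ii.1 keeps that hidden until the evaluations are complete. Reword the conjunction in section I to match the order. As a note, say in IV.c.i.1 and IV.g.i that the 80 % power applies to K18-UDMA versus no sealant.

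**Cost.** Wording only, with no added patients or procedures. The sized contrast keeps its full power, unlike under a six-way Bonferroni split. The drawback is that lesion depth cannot support a confirmatory claim. The order is a choice. This one follows the contrast the trial was sized on, and another prespecified order would also close the gap.

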- iv. When the patient reports to the oral surgeon for extractions, the extracted teeth will be placed in Tooth Storage Solution which is antimicrobial and does not alter the surfaces or composition of the teeth. The container will have the patient number and date of extraction written on the label.
- v. There is no difference related to the procedures used to extract the teeth that are to be extracted for orthodontic therapy. The standard of care is the same for all patients whether there is a sealant or not on the teeth to be extracted.
- vi. These teeth will be returned to the laboratory for histological evaluation of mineral density and lesion depth.
- vii. The original location of the extracted teeth can be easily made from the tooth morphology. The source of the extracted tooth (original location and patient number) will be recorded in the laboratory notebook, and when data evaluation is conducted will be used to identify the experimental group for that the tooth.

d. Description, Risks and Justification of Procedures and Data Collection Tools:

- i. Description: These experiments utilize bicuspid that are treatment planned for extraction to allow for an approximant 30-day period where the experimental treatment is exposed to the environment of the mouth in exactly the same manner as all other teeth in the patients mouth.

1. About 30 % of the patients who receive treatment planning for orthodontic therapy will require extraction of bicuspid.
2. The extractions are usually scheduled to occur at about 30 days after bracket bonding to the other teeth.
3. The experimental design requires that each patient will have all experimental and control conditions (on separate teeth). This split mouth paired samples design increases the power of the experiment and allows for fewer patients to be required for sufficient statistical power. Paired analyses within an individual renders greater sensitivity to experimental effects than population based analyses.
4. Bonding bracket pads instead of full brackets removes the protruding portion of the bracket so that it does not interfere with the orthodontic wires that are placed for the therapy.

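### Optional fourth-tooth location analysis: the only named tests take one treatment at a time, so no K18-versus-no-sealant contrast between arches is named and at least half of the teeth stay outside this analysis

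*Combined protocol and SAP*

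**What the plan says.** Two places give the fourth tooth a purpose, and the purposes differ.

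- Section IV.c.i, item 2 (study design), on giving a random treatment to a fourth bicuspid: "This will provide additional information on the effect of location (upper or lower jaw) on the protective ability of the experimental sealant".
- Section IV.f.iii (data analysis plan): "Secondary analyses may be possible to assess the ability of microbial biofilm to cause demineralization differences between upper and lower arches". The fourth tooth repeats one treatment, and the stated purpose of assigning one of the "three treatments will be to generate a pair (left vs. right or upper vs. lower) for comparison".

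The only method named for this is in IV.f.iii: "The statistical analyses will include paired-t tests for the differences that may be observed within each treatment group".

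Other relevant text:

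- IV.f.i, on the main comparison, confirms that a fourth tooth produces one duplicated treatment ("Should there be data from a 4th tooth (2 teeth will receive the same treatment"). The two values are averaged before treatments are compared. The ANOVA there is one-way, by treatment.
- IV.f.ii: "The possibility of regional variations (left vs. right, upper vs. lower) has been taken into account in the calculation of the size" of the cohort, by way of 10 extra patients.
- IV.b admits patients with three or more planned bicuspid extractions. IV.f.iii calls a fourth usual but gives no figure.
- IV.c.vii: "The source of the extracted tooth (original location and patient number) will be recorded in the laboratory notebook".

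**The concern.** Protective ability is a comparison: sealed teeth against unsealed teeth. Whether it depends on the jaw is therefore a question about a difference of differences, the K18-minus-no-sealant effect in the upper arch against the same effect in the lower arch. A paired t-test within K18 shows whether K18 teeth differ between arches. It cannot separate a sealant that works less well in one arch from an arch that demineralizes more whatever is placed on the tooth. That needs the no-sealant teeth in the same estimate.

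As written, a reader would have up to three within-treatment results, each from a few pairs, and would compare them by eye. One significant and one non-significant result could then be read as a jaw effect on protection, which such a comparison does not show. Teeth without a same-treatment partner would add nothing, although their location, patient and treatment are known.

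**Working it through.** **The plan's own figure.** No sample size or power is stated for the location analysis. The only calculation is for the main comparison: 20 subjects, 80 % power, alpha 0.05, a 10 % difference in mineral density (IV.c.i, item 1). No SD is given, so 20 cannot be reproduced, only back-solved. For a two-sided paired t-test (sidedness assumed) with n = 20, the detectable standardized difference is 0.660, so SD = 10 / 0.660 = 15.1 points. I use this as an assumption. The 50 % addition is consistent: 20 × 1.5 = 30.

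**Teeth entering the location tests.** Four teeth and three treatments, each used at least once, give exactly one same-treatment pair. Three teeth give none. With N patients and a share p with four bicuspids, there are N(3 + p) teeth, of which 2pN are in pairs. The share outside is 1 − 2p/(3 + p):

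- p = 1: 1 − 2/4 = 50 %
- p = 0.75: 1 − 1.5/3.75 = 60 %
- p = 0.5: 1 − 1/3.5 = 71 %

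So one half is the floor, even if left-right pairs are counted.

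**Upper-lower pairs per treatment.** Assume one bicuspid per quadrant. There are 36 possible assignments: 12 give a left-right pair, 12 a same-side upper-lower pair and 12 a diagonal pair. The placement diagram is not readable, so I take three cases with N = 20, p = 1 and treatments repeated equally often:

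- all repeats placed upper-lower: 20 × 1/3 = 6.7 pairs per treatment
- fully random, diagonals counted: 20 × 2/9 = 4.4
- evenly split between left-right and upper-lower: 20 × 1/6 = 3.3

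These numbers fall in proportion to p.

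**Precision, like for like.** With m pairs per treatment, the paired SE within K18 is 15.1/√m. The best that the planned tests offer for the jaw-by-sealant question is to subtract the no-sealant result from the K18 result, with SE 15.1 × √(2/m). The alternative is least squares on all 80 teeth with patient as a fixed effect plus treatment, arch, side and treatment-by-arch. Its tooth-level SD is 15.1/√2 = 10.7, and its error df are 80 − 20 − 6 = 54 (t = 2.005). Model SEs are averages over simulated designs and move by about 0.1 between runs.

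| Placement | m | Within K18: paired | Within K18: model | Contrast: paired | Contrast: model |
|---|---|---|---|---|---|
| All upper-lower | 6.7 | 5.9 | 4.6 | 8.3 | 6.6–6.7 |
| Fully random | 4.4 | 7.2 | 4.9 | 10.2 | 7.4 |
| Even split | 3.3 | 8.3 | 5.1 | 11.7 | 7.6–7.7 |

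For the contrast, the paired SE is larger by a factor of about 1.2 (8.3/6.7) to 1.5 (11.7/7.7). The model's 95 % half-width is 2.005 × 6.6 = 13.2 to 2.005 × 7.7 = 15.4 points.

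**Sensitivity.**

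- If half of the K18-versus-no-sealant variance is patient-by-treatment variation (same-treatment difference SD 10.7), and a random-patient model allows for it, the contrast SEs are 5.9 versus 5.2 (all upper-lower), 7.1 versus 5.9 (random) and 8.3 versus 6.4 (even split). The smallest gain is then about 1.1-fold.
- An SD of 10 to 20 multiplies every SE by 0.66 to 1.32. The half-width then runs from about 9 (13.2 × 0.66) to about 20 (15.4 × 1.32) points.

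**The case against.** The plan has a fair defence. IV.f.iii says analyses may be possible and will include paired t-tests, so it is neither binding nor exclusive. Its own aim, differences between arches, is directly addressed by same-treatment pairs, and nothing planned there is invalid. The design section promises only additional information and names no comparator, and upper against lower K18 teeth in one patient is information of that kind. Matched pairs are a deliberate choice (IV.b and IV.d). All of this stands. It limits the point to a missing contrast and lost precision, in an analysis for which no power is claimed.

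Four stronger readings are tempting but not supported:

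- *Half of the specimens are wasted.* They are not. Under IV.f.i every tooth enters the main comparison, with duplicates averaged. Only the location analysis leaves teeth out.
- *The plan expects regional effects and ignores them.* IV.f.ii speaks of a possibility and answers it with 10 extra patients, and placement is set by computer randomization. An arch or side term could add precision; its absence from the main analysis is not an error.
- *The paired tests are hopelessly imprecise.* With 4 pairs the within-K18 half-width is 7.57 × 3.18 = 24 points, but much of that is the t quantile on 3 df. With 7 pairs it is 5.72 × 2.45 = 14, against about 9 for the model (2.005 × 4.6).
- *A model would settle whether protection differs by jaw.* It would not. Its half-width exceeds the plan's 10 % relevant difference under the back-solved SD.

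A random patient effect would also bring in some between-patient information, which departs from the matched-pair principle. Fixed patient effects avoid this at a small cost: the contrast SE is about 7.4 to 7.7 instead of 7.0 to 7.2 under random or even-split placement.

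**Conclusion.** The point holds as a minor one. For the optional location analysis, the only named tests estimate a location difference under one treatment at a time. They fit IV.f.iii's arch aim, inform the design section's aim only indirectly, and leave at least half of the teeth out of this analysis. The tooth count follows from the design alone.

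The precision figures (contrast SE about 6.6 to 7.7 by the within-patient model, 8.3 to 11.7 by subtracting paired results) rest on a back-solved SD of 15.1, 20 patients with four bicuspids each, one bicuspid per quadrant and assumed placement patterns. The gain is smallest if all repeats are placed upper-lower or if patient-by-treatment variation is large. The interaction stays imprecise in every case, and the main sealant comparison is not affected.

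**What to change.** State both location aims together in IV.f.iii and, for this secondary analysis only, replace the within-group paired t-tests with wording such as:

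> Exploratory: outcomes from all individual teeth will be analysed in a linear model with patient (fixed effect, so that comparisons stay within patient; a random effect as a check), treatment, arch, side and treatment-by-arch. The upper-lower difference (overall and within K18) and the K18-versus-no-sealant by arch interaction will be reported with 95 % confidence intervals.

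As a further check, add a patient-by-treatment random effect and treatment-specific residual variances if they can be estimated. Present the interaction as an estimate, not as a test of efficacy by jaw.

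The cost is wording and a little analysis time. No extra teeth or measurements are needed, because location and patient number are already recorded. The downsides are that the model assumes a common residual variance and an additive side effect, and that the interaction interval will still be wide.
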